Subjects who do not wear glasses will be given study spectacles without any optical correction. Subjects who already wear glasses will be given customized spectacles that incorporate their optical correction. Subjects who customarily wear contact lenses will be asked to wear glasses without an optical correction over their contact lenses.

The optical properties of the thin film coating and the gray tint are shown in Figure 2. All spectacles will have the same overall optical density across the visible spectrum. This statement means that all study eyewear will appear to have the same amount of “darkness” to the subject. The total study duration will be 16 weeks

Table 1. Protocol Visit Schedule

Visit	Week	Activities
1	0	Determine eligibility
		Informed Consent
		HIT-6
		Baseline photophobia and ADL questionnaire
		Receive diary
		Randomization
2	4	Diary check
		HIT-6
		Receive glasses/Check glasses fit
3	8	Diary check
		HIT-6
		Check glasses fit

4	12	Diary check
		HIT-6
		Check glasses fit
5	16	Diary check
		HIT-6
		Final photophobia, ADL and masking questionnaires
		Keep glasses OR receive compensation and return glasses

Baseline Visit 1 (Week 0)

Subjects who meet study inclusion and exclusion criteria will be invited to participate in the study. Potential subjects will have all of their questions about the study answered. Subjects who agree to participate will sign an informed consent document and be given a copy of the document. They will fill out a baseline questionnaire regarding light sensitivity and activities of daily living (Figure 3). They will complete the 6-item Headache Impact Test (HIT-6; Figure 4) The HIT-6 is copyrighted, but its use is not restricted by the holder of the copyright and it's not necessary to get permission or pay the copyright holder for use of the questionnaire. At the discretion of the site PI or coordinator, this visit may be completed by phone. Study materials including the informed consent document and questionnaires may be transmitted by U.S. mail, email, or fax.

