Subjects will be randomized with equal allocation to receive either tinted or thin-film coated spectacles. A random permuted block randomization will be employed. However, before receiving their study spectacles, subjects will complete a four-week "baseline period" during which no study lenses will be worn. This period will help establish the base-line characteristics of their headaches. Subjects will keep daily diaries throughout the 16-week study detailing the frequency and severity of their headaches (Figure 5).

Visit 2 (Week 4)

When subjects return after the 4-week baseline period, the research team will review their diaries. Subjects must provide at least 20 days of diary data and must have had at least 15 headache days (defined as a calendar day consisting of at least 4 hours of continuous headache). This requirement helps insure subjects meet the definition of chronic migraine. Subjects must have had at least 4 distinct headache episodes each lasting at least 4 hours during the 4-week baseline period. This requirement helps insure that subjects with continuous headache are not included in the study, as these subjects are often unresponsive to any headache treatments. Subjects whose diaries do not meet these criteria will exit the study. Subjects whose diaries indicate that they are overusing abortive pain medications will exit the study. Subjects who exit the study at this point will be given a \$25 gift card. At the discretion of the site PI or coordinator, this visit may be completed via phone. Study instruments including the diaries and questionnaires may be completed by phone or transmitted by U.S. mail, email or fax. Alternatively, these instruments may also be completed by the participant within REDCap.

Subjects whose diaries meet these criteria will complete a questionnaire and receive their study spectacles. The research team will insure the glasses fit comfortably and will instruct the subjects to wear them full time. Subjects will receive new diaries.

Visit 3 (Week 8)

The research team will review the subject's diaries, insure the subject's glasses still fit comfortably, and will instruct the subject to continue to wear the glasses full-time. Subjects will complete a questionnaire and receive new diaries. At the discretion of the site PI or coordinator, this visit may be completed via phone. Study instruments

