In a secondary analysis, generalized estimating equations (GEE) will be applied to a generalized linear model in which the probability of reporting a headache day during the treatment period is related to a) the baseline frequency of headache days, b) the randomized treatment group, c) week of follow-up, defined as a categorical variable, and d) the interaction of the randomized treatment group with follow-up week. This analysis will be used to characterize the treatment effect over different portions of the follow-up period. A binary outcome model with a logistic link function will be used. A compound symmetry working covariance matrix will be applied and robust standard errors will be used for statistical inferences. The analysis will provide estimates of the odds ratio (with associated 95% confidence intervals and p-values) for reporting a headache day between the two treatment groups obtained separately for each follow-up month. If the interaction between the randomized treatment group and week of follow-up is not statistically significant at the $\alpha=0.05$ level, an overall estimate of the odds ratio for reporting a day with severe headache between the two treatment groups will be provided under a reduced model which excludes the randomized treatment group by follow-up week interaction. For reporting purposes, we will

also provide ratios of the probabilities for reporting headache days using a marginal means approach, with bootstrap resampling used to estimate 95% confidence intervals and p-values.

Analysis of HIT-6

The main secondary analysis of the HIT-6 Total Score will be performed using a linear mixed effects model for a normally distributed outcome. The mixed effects model will relate the mean HIT-6 scores at weeks 4, 8, 12, and 16 of treatment to a) the baseline (week 0) HIT-6 score, b) the randomized treatment group, c) the follow-up visit, defined as a categorical variable, and d) the interaction of the randomized treatment group with follow-up visit. An unstructured covariance model will be used to account for repeat observations over the three follow-up assessments. The main contrast to evaluate the treatment effect will compare the mean HIT-6 scores over the 4, 8, 12 and 16 week visits; additional exploratory contrasts will compare the HIT-6 scores at weeks 4, 8, 12, and 16 individually.

Sample Size and Power

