In a subgroup of 22 subjects with at least 50% and less than 100% headache days in our pilot crossover trial, the pooled mean \pm standard deviation for the follow-up % of headache days across the two periods was 69.0% \pm 18.6%. We observed a Pearson correlation of 0.55 between the baseline and follow-up % of headache days. Assuming the same means and standard deviations, and allowing for 10% loss-to-follow-up, 140 randomized subjects (70 for each treatment group) will provide 80% power with 2-sided $\alpha=0.05$ to detect a mean reduction in the % of headache days of 7.8%. This would represent, for example, a decrease from 69.0% headache days to 61.2% headache days.

The effect size of 7.8% is under half the assumed follow-up standard deviation of 18.6% points, and thus represents a moderate effect size.

Other Secondary Outcomes

To measure severity of headaches, we will use the subjects' daily diaries to count the number of days with headache that either a) made activity difficult, b) caused activity changes, or c) caused patient to go to bed. We will compare the proportion of days that are free of headaches leading to any one of these three criteria using the same GEE approach that was described for the sensitivity analysis of the frequency of headache days.

Exploratory Outcomes

- a. Proportion of subjects who were able to move out of the "very severe impact" category of the HIT-6 between baseline and the three follow-up assessments.
- b. Proportion of patients who experienced at least a 5-point improvement in their HIT-6 score from baseline to each of the three follow-up assessments (weeks 8, 12, and 16).
- c. Proportion of days that are free of headaches that require use of medications to control the headache over the 12-week intervention.
- d. Proportion of days with light sensitivity over the 12-week intervention.
- e. Average Number of Hours Slept per night over the 12-week intervention.

Subject participants ages 18-22 years ("transitional adolescents")

We are interested in the comparative effectiveness of tints and coatings in the treatment of migraine within this age group. Enrollment and randomization will be stratified within this age group to allow a statistical analysis for this subgroup. Subjects in this age group will have a separate block randomization. Based on previous experience, we anticipate enrolling 6-8 subjects in this age group.

Analysis Plan for Secondary and Exploratory Outcomes

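### The HIT-6 model treats the pre-lens Week 4 score as a treatment outcome and adjusts only for Week 0; using both pre-lens scores as covariates is a cheap gain in precision

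*Combined protocol and SAP*

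**What the plan says.** Section 4 (Study Information), item 9, Analysis of HIT-6, sets out the model. "The mixed effects model will relate the mean HIT-6 scores at weeks 4, 8, 12, and 16 of treatment to" a list of terms in which the only HIT-6 covariate is "the baseline (week 0) HIT-6 score"; the others are treatment group, visit as a category, and their interaction. The contrast is stated as: "The main contrast to evaluate the treatment effect will compare the mean HIT-6 scores over the 4, 8, 12 and 16 week visits". The same paragraph counts the visits differently: "An unstructured covariance model will be used to account for repeat observations over the three follow-up assessments".

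The schedule in item 6 places Week 4 before treatment. The first four weeks are a baseline period "during which no study lenses will be worn". In Table 1, Visit 2 (Week 4) lists the HIT-6 on the line above "Receive glasses/Check glasses fit". The Visit 2 text likewise has subjects complete a questionnaire and receive their spectacles at that visit.

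The Exploratory Outcomes in item 9 agree with the schedule. Outcome b is assessed at "each of the three follow-up assessments (weeks 8, 12, and 16"), which leaves Week 4 out of follow-up.

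**The concern.** Two HIT-6 scores are collected before any lens is worn. The model uses the earlier one as a baseline and places the later one, the closer of the two to the start of treatment, on the outcome side. The primary analysis of headache days works differently: its covariate covers the whole four-week pre-lens period.

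At stake is the precision of the main secondary outcome, which is tested at two-sided 0.05 with no stated power. A noisy patient-reported score is predicted better by two earlier readings than by one. If Week 4 were simply deleted from the contrast and nothing else changed, its baseline information would still be lost. The choice of covariate is therefore a separate step from correcting the list of visits.

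**Working it through.** **The plan's own figure.** There is none for HIT-6. The only power statement concerns headache days, and it reproduces. The adjusted SD is 18.6 × √(1 − 0.55²) = 15.53. Then n = 2 × (1.96 + 0.8416)² × 15.53² / 7.8² = 62.3, so 63 per arm, and 63 / 0.9 = 70 per arm, or 140 in total. This calculation is sound, but it says nothing about HIT-6.

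**Inputs for HIT-6.** The visits, covariate and contrast are those quoted above. The correlations are assumed, because the documents give none; their 0.55 is for headache days. The main case takes equal variances (set to 1), one correlation r between any two visits, and complete data.

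**Step 1: does Week 4 help as an outcome?** With its own treatment-by-visit term and an unstructured covariance, Week 4 has a free treatment effect, so it places no constraint on the later visits. I computed the generalised least squares variance of the Weeks 8 to 16 contrast with 63 per arm, r = 0.5, known covariance and a common slope on Week 0. With Week 4 as an outcome, the variance was 0.999 times the variance without it. With complete data it adds essentially nothing.

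**Step 2: Week 4 as a covariate.** Residual variance of the mean of Weeks 8, 12 and 16:

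- given Week 0 only: A = (1 + 2r)/3 − r²
- given Weeks 0 and 4: B = (1 + 2r)/3 − 2r²/(1 + r)

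At r = 0.5, A = 0.6667 − 0.25 = 0.417 and B = 0.6667 − 0.3333 = 0.333, a ratio of 0.80.

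**Step 3: the contrast as written.** The mean of Weeks 4, 8, 12 and 16 given Week 0 has variance P = (1 + 3r)/4 − r². Week 4 can carry no lens effect, so this contrast estimates 3/4 of an effect that is constant over Weeks 8 to 16. On the scale of that effect its variance is P / 0.75². At r = 0.5, P = 0.375 and P / 0.5625 = 0.667.

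| r | A | B | saving, B against A | P / 0.75² | saving, B against P / 0.75² |
|---|---|---|---|---|---|
| 0.2 | 0.427 | 0.400 | 6% | 0.640 | 38% |
| 0.3 | 0.443 | 0.395 | 11% | 0.684 | 42% |
| 0.4 | 0.440 | 0.371 | 16% | 0.693 | 46% |
| 0.5 | 0.417 | 0.333 | 20% | 0.667 | 50% |
| 0.6 | 0.373 | 0.283 | 24% | 0.604 | 53% |
| 0.7 | 0.310 | 0.224 | 28% | 0.507 | 56% |

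**Step 4: splitting the larger saving.** At r = 0.5, dropping Week 4 from the contrast takes the variance from 0.667 to 0.417 (37.5%). Adding it as a covariate takes it on to 0.333 (50% in all). Over r = 0.4 to 0.7 the first step alone saves 37% to 39%, so most of the larger figure comes from the visit list.

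**Step 5: sensitivity to the correlation pattern.** Let the correlation at lag k be r × f^(k−1), with adjacent r from 0.5 to 0.8 and f from 0.8 to 0.9. The ratio B/A is then 0.73 to 0.85, a saving of 15% to 27%.

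**Step 6: in terms of power.** An effect with 80% power under A has Φ(2.80/√(B/A) − 1.96) under B, which is 86% at r = 0.4 and 91% at r = 0.7. If instead B has 80% power, A has about 73% to 66% and the contrast as written about 54% to 46%.

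**The case against.** **The plan uses Week 4.** A reader might infer that the model ignores the score. It does not: Week 4 is modelled as an outcome and averaged into the main contrast. What is unused is its role as a baseline.

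**The 16% to 28% is not measured against the written contrast.** This stands. It compares two analyses of Weeks 8, 12 and 16, a contrast that the HIT-6 paragraph does not state, although its own count of three assessments and exploratory outcome b point to it. Against the written contrast without rescaling, the saving is only 5%, 11% and 22% at r = 0.4, 0.5 and 0.7. That comparison, however, sets a diluted effect beside an undiluted one.

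**The size rests on an assumption.** This also stands. No HIT-6 SD or correlation is given, and at low correlations the gain is modest.

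**Missing data.** With dropout, a Week 4 outcome does help inform missing later visits, so Step 1 holds strictly for complete data. The plan allows for 10% loss. As a covariate, Week 4 would also inform those visits.

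**Timing.** Randomization is at Visit 1, and only the order of rows in Table 1 puts the HIT-6 ahead of dispensing. The Visit 2 text lets instruments be returned by phone, mail, email, fax or REDCap. A form filled in after lens wear began would be a post-treatment covariate. This calls for a date check; it does not defeat the proposal.

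**The responder outcome.** A reader might infer that the 5-point outcome ("Proportion of patients who experienced at least a 5-point improvement in their HIT-6 score from baseline") is distorted by run-in change and regression to the mean. These are expected equally in both randomized arms, and the outcome is exploratory, so no change to it is needed.

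**Conclusion.** The point holds as a cheap improvement to the main secondary analysis. The HIT-6 model places a pre-lens score among the treatment outcomes and adjusts for only one of two available baselines. Under an assumed common correlation of 0.4 to 0.7 and complete data, using both lowers the variance of the Weeks 8 to 16 contrast by about 16% to 28% (6% to 11% at 0.2 to 0.3; 15% to 27% under the decaying patterns tried). Compared with the written contrast, rescaled for a post-lens effect constant over Weeks 8 to 16, the total saving is about 46% to 56% at 0.4 to 0.7.

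A reader might go further and infer that adjusting for Week 0 alone biases the treatment comparison. It does not: under randomization, one-baseline adjustment is valid and merely less precise. The 0.75 dilution is a different matter. It comes from averaging Week 4 into the contrast, not from the choice of covariate. The primary analysis is unaffected, and no stated HIT-6 power figure is contradicted because none exists.

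**What to change.** In Analysis of HIT-6:

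- Model only Weeks 8, 12 and 16 as outcomes and define the main contrast over those visits, in line with the count of three assessments and exploratory outcome b.
- Enter the Week 0 and Week 4 HIT-6 scores as two covariates.
- Use the Week 4 score only if it was completed before lens wear began. Otherwise treat it as missing and fill it by a baseline imputation that ignores treatment arm.
- Amend the Numeric outcomes paragraph, which carries the same list of four visits into other outcomes analysed this way.

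The cost is one covariate degree of freedom, a check of completion date against dispensing or first wear, and a rule for missing values. No new data are needed. Missing Week 4 scores should be few, since subjects must pass Visit 2 to receive lenses. The wording should be settled before unblinded data are seen.

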9. Provide a summary of the statistical methods, data analysis, or data interpretation planned for this study. Factors for determining the proposed sample size (e.g., power) should be stated.

Preliminary Analyses

Baseline characteristics will be summarized by randomized treatment group with standardized differences between treatment groups used to assess the balance of patient characteristics between the two groups. Univariate summaries will also be performed at baseline and follow-up for the primary and secondary outcome variables. If quantitative outcome variables exhibit substantial skewness, transformations may be sought to better approximate normality.

Primary Analysis of Headache Days

The primary analysis of the efficacy of the thin-film intervention will be conducted as an analysis of covariance comparing the proportion of days during the 12 week follow-up period recorded as headache days between the thin-film treatment group and the tinted glasses group, using the proportion of headache days during the 4-week baseline as a covariate. The null hypothesis of no treatment effect on headache frequency will be rejected if the 2-sided p-value corresponding to the treatment effect is smaller than 0.05.

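### Ages 18-22 are randomized from their own block list, but none of the specified models has a term for that stratum

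*Combined protocol and SAP*

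**What the plan says.** All references are to the combined protocol and SAP, section 4 (Study Information).

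- **Randomization.** Item 6, Baseline Visit 1, sets equal allocation: "A random permuted block randomization will be employed". Item 9, in the paragraph on ages 18-22, makes that age group a stratum: "Enrollment and randomization will be stratified within this age group to allow a statistical analysis for this subgroup", and "Subjects in this age group will have a separate block randomization". The expected size is small: "we anticipate enrolling 6-8 subjects in this age group".
- **Primary analysis** (item 9, Primary Analysis of Headache Days). The ANCOVA compares the two lens groups "using the proportion of headache days during the 4-week baseline as a covariate". No other covariate is named.
- **GEE** (same item). The listed terms are "a) the baseline frequency of headache days, b) the randomized treatment group, c) week of follow-up, defined as a categorical variable", plus treatment by week.
- **HIT-6 mixed model** (same item, Analysis of HIT-6). The listed terms are "a) the baseline (week 0) HIT-6 score, b) the randomized treatment group, c) the follow-up visit, defined as a categorical variable", plus treatment by visit.
- **Other outcomes.** The severity outcome and the diary-proportion outcomes reuse the GEE, and numeric outcomes reuse the mixed model. No term is added in either case.

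The plan names no method for the analysis within ages 18-22. It claims no power for that analysis and sets no decision rule.

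**The concern.** When allocation is balanced within a stratum, an analysis that ignores the stratum leaves its between-stratum variation in the residual. If age group predicts headache frequency after baseline adjustment, the standard error of the treatment effect is then slightly too large and some power is lost. The model terms are listed explicitly, so as written the analysis does not match the randomization. Leaving the term out of the plan also leaves open a later choice about whether to adjust. What needs establishing is how much power is at stake and whether the type I error is affected.

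A second, smaller matter is that the stated reason for stratifying is a comparison within 6-8 subjects, and the plan does not say how that comparison will be reported.

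**Working it through.** **Inputs from the plan** (item 9, Sample Size and Power): follow-up SD 18.6 points, baseline to follow-up correlation 0.55, difference 7.8 points, two-sided alpha 0.05, and "allowing for 10% loss-to-follow-up, 140 randomized subjects", 70 per group. The stratum holds 6-8 of 140, or 4.3-5.7%.

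**Step 1: reproduce the plan's figure.**
- Residual SD after baseline adjustment = 18.6 × √(1 − 0.55²) = 15.53.
- Evaluable subjects = 140 × 0.9 = 126, or 63 per group.
- Power for 7.8 points at 63 v 63 is 79.8% by noncentral t and 80.5% by normal approximation. The stated 80% reproduces with baseline as the only covariate.

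**Step 2: variance left in the residual.** With stratum fraction p and a baseline-adjusted age difference d, omitting the term inflates the residual variance by p(1 − p)d²/15.53². The plan gives no d, so 5, 10 and 20 points are assumed.
- d = 5: 0.4-0.6%.
- d = 10: 1.7-2.2%. For 8 of 140, 0.0571 × 0.9429 × 100 / 241.3 = 2.2%.
- d = 20: 6.8-8.9%. This value of d exceeds the plan's own SD of 18.6.

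**Step 3: simulate the primary ANCOVA.** 140 subjects were randomized with separate permuted blocks of 4 in each stratum (block size assumed, as none is given). Each subject was lost with probability 0.10, the data were normal, and there were 100,000 runs per cell. Entries are percentages.

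| Number aged 18-22 | Age difference | Power, term omitted | Power, term included | Type I error, term omitted |
|---|---|---|---|---|
| 6 | 0 | 79.32 | 79.25 | 5.06 |
| 6 | 5 | 79.56 | 79.54 | 5.07 |
| 6 | 10 | 78.82 | 79.29 | 4.74 |
| 6 | 20 | 77.17 | 79.29 | 4.58 |
| 8 | 0 | 79.50 | 79.44 | 5.01 |
| 8 | 5 | 79.25 | 79.37 | 4.98 |
| 8 | 10 | 78.97 | 79.60 | 4.78 |
| 8 | 20 | 76.76 | 79.35 | 4.22 |

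Omitting the term costs about 0-0.1 power points at d = 5, 0.5-0.6 at d = 10 and 2.1-2.6 at d = 20. Including it when age does not matter costs less than 0.1. With the term included, type I error is 4.8-5.1% throughout. The Monte Carlo standard error of a type I error entry is about 0.07 points, so values slightly above 5% are nominal.

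**Step 4: the 18-22 comparison.** This assumes that the pilot SD and correlation apply at these ages and that nobody is lost. Half-width = t(0.975, n − 3) × 15.53 × √(1/n₁ + 1/n₂).

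| Split | t | 95% CI half-width (points) | Power for 7.8 points |
|---|---|---|---|
| 3 v 3 | 3.18 | 40.4 | 7.3% |
| 3 v 4 | 2.78 | 32.9 | 8.1% |
| 4 v 4 | 2.57 | 28.2 | 9.0% |

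If the residual SD is 25% lower or higher, the half-width ranges from 21 to 51 points and power from 6.5% to 12.2%. At 10% loss, 5.4-7.2 of the 6-8 are expected to remain (6 × 0.9 and 8 × 0.9), so these figures lean optimistic.

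**The case against.** The strongest reply is that the effect is close to nil. The only visible loss needs a 20-point age difference that survives baseline adjustment, which is 20/15.53 = 1.3 residual SDs, and nothing in the plan suggests a difference of any particular size. Baseline headache frequency is already in the ANCOVA and would absorb part of any age difference. This stands, and it is why the point is minor.

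It can also be said that the stratification serves the subgroup analysis and not balance in the main comparison, so the omission contradicts nothing in the plan. That is true of the motive. The motive does not change the allocation, which is still balanced by stratum.

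The figures cover the ANCOVA only. In the logistic GEE, adding a prognostic covariate changes the odds ratio being estimated as well as its precision. That is correct, and the size of the shift was not computed. With 4-6% of subjects in the stratum it should be slight, and the plan also reports marginal probability ratios.

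On the subgroup, the half-width formula ignores chance baseline imbalance between very small arms. Simulating the ANCOVA gives median half-widths of 40.4, 33.0 and 28.4 points and means of 43.5, 34.9 and 29.6. Blocks of 4 could also split six subjects 4 v 2. The tabulated figures are therefore approximate and, if anything, flattering. Wide intervals would not hide a very large difference; they do rule out resolving one near 7.8 points.

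**Conclusion.** The concern holds and is minor. Ages 18-22 form a randomization stratum, and none of the three specified models, nor the analyses that reuse them, contains it. Without the term the primary test remains valid, with type I error of 4.2-5.1%, and the trial's conclusions are not threatened. The gain from adding it is under one power point for an age difference up to 10 points and 2.1-2.6 points at 20, and there is essentially no penalty if age is irrelevant. These results rest on assumed age differences, an assumed block size of 4, normal data and loss at random.

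The subgroup remark is a secondary reporting note. The interval half-width is about 3.6 to 5.2 times the planned effect (28.2/7.8 and 40.4/7.8), so the 18-22 estimate will be descriptive.

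**What to change.** Add an indicator for the randomization stratum (18-22 versus over 22) as a fixed effect in the primary ANCOVA, the GEE, the HIT-6 mixed model and the secondary and exploratory analyses that reuse the last two. For the GEE, state that the odds ratios are conditional on the stratum, and include the stratum in the marginal-means step.

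State that the 18-22 comparison will be reported as an exploratory estimate with a 95% confidence interval, and that no conclusion about which lens is better in that age group will be drawn from it.

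The cost is a few lines of SAP wording and one degree of freedom per model. The sample size stays at 140, and randomization and data collection are unchanged.

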Outcomes defined as proportions of days meeting designated criteria based on diary information. Analyses of secondary and exploratory outcomes defined by proportions of days during the follow-up period that satisfy designated conditions will be carried out using the same GEE approach that was described for the secondary analysis of the proportion of headache-free days. Thus, for each outcome, we will estimate the treatment effect separately during each of the four follow-up months as well as the overall effect across all 4 follow-up months.

Numeric outcomes. Descriptive summaries and graphical displays using histograms will provide numeric outcome variables at baseline and over the respective follow-up assessments, by treatment group. Transformations may be sought to better approximate normality for outcomes exhibiting substantial skewness. Numeric secondary and exploratory outcomes that are assessed at baseline and the week 4, week 8, week 12 and week 16 follow-up visits will be analyzed using the linear mixed effects modeling approach described for the HIT-6 score.

Multiple comparisons. Both the primary and the main secondary outcomes will be compared between the randomized groups using a 2-sided α -level of 0.05. Additional secondary and exploratory outcomes will also be compared between the treatment groups using a 2-sided α level of 0.05, without adjustment for multiple comparisons. However, all results from these analyses will be interpreted as exploratory and will take into account the risk of Type 1 errors resulting from multiple hypothesis tests.

Missing Data. The computation of the % of headache days will include only those days with non-missing headache diary information. This analysis will remain approximately unbiased as long as the days on which headache status is recorded in the diaries are independent of actual headache status. The analysis of the HIT-6, which is based on a linear mixed effects model, will be approximately unbiased so long as the pattern of missing data is missing at random, meaning that the probability that an outcome measurement is missing may depend on the values of other non-missing measurements, but not on the value of the missing measurement itself. If the fraction of missing HIT-6 scores exceeds 10% at any given follow-up visit, multiple imputation will also be applied prior to the analysis of the main secondary HIT-6 outcome.

Interim Analysis.

No formal interim analyses for efficacy will be performed.

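### The GEE reused for the severity, medication-day and light-sensitivity outcomes names only baseline headache-day frequency as its baseline covariate; the plan should state that each outcome's own run-in proportion enters

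*Combined protocol and SAP*

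**What the plan says.** All references are to section 4, Study Information, unless stated otherwise.

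- **The template.** Item 9, Primary Analysis of Headache Days, defines a secondary GEE with a logistic link. The probability of a headache day "is related to a) the baseline frequency of headache days, b) the randomized treatment group, c) week of follow-up"; the fourth term is the treatment-by-week interaction. Headache-day frequency is the only baseline measurement in the list.
- **Severity.** Item 9, Other Secondary Outcomes, compares the proportion of days free of activity-limiting headache "using the same GEE approach that was described for the sensitivity analysis of the frequency of headache days".
- **Other diary proportions.** Item 9, Exploratory Outcomes, lists "Proportion of days that are free of headaches that require use of medications to control the headache over the 12-week intervention" and "Proportion of days with light sensitivity over the 12-week intervention". The Analysis Plan for Secondary and Exploratory Outcomes says that analyses of such outcomes "will be carried out using the same GEE approach that was described for the secondary analysis of the proportion of headache-free days". Neither cross-reference names a baseline covariate.
- **The other models.** The primary ANCOVA adjusts for the baseline proportion of headache days, and the HIT-6 mixed model for the week 0 HIT-6 score. Each uses the baseline of its own outcome.
- **The data.** Item 6, Baseline Visit 1: "Subjects will keep daily diaries throughout the 16-week study detailing the frequency and severity of their headaches". This covers the 4-week run-in. Visit 2 judges overuse of abortive medication from the same diaries.

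**The concern.** An analyst who follows the cross-references to the letter would fit the severity, medication and light-sensitivity models with the headache-day baseline and no baseline of the outcome itself. The proportion of run-in days meeting an outcome's own criterion is often the best single predictor of the same proportion at follow-up. Leaving it out gives up precision for no saving, at least for severity and medication use, where the documents show that the run-in data exist.

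Severity is a named secondary outcome, and light-sensitivity days are a daily measure of the symptom that motivates the lenses. All of these outcomes are tested at a two-sided 0.05 level.

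There is also a specification issue. Where a plan does not settle the covariate, it can be chosen after results are seen.

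**Working it through.** **1. Reproduce the plan's figure (headache days).** Inputs from item 9, Sample Size and Power: follow-up SD 18.6 points, baseline to follow-up correlation 0.55, difference 7.8 points, 140 randomized, 10% loss, 80% power, two-sided α = 0.05.

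- Residual SD = 18.6 × √(1 − 0.55²) = 18.6 × √0.6975 = 15.53.
- n per arm = 2 × (1.960 + 0.842)² × 15.53² / 7.8², which rounds up to 63. Then 126 / 0.9 = 140. Power at 63 per arm is 80.5% (79.8% by noncentral t). The plan's figure is reproduced.
- With no baseline covariate (SD 18.6), 63 per arm give 65.3% power, and 200 subjects would be needed. For headache days the matching baseline is therefore worth about 15 percentage points of power.

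**2. Compare the two candidate covariates.** Let r_own be the correlation of an outcome's run-in proportion with its follow-up proportion, and r_hd that of baseline headache-day frequency with the same follow-up proportion. With one covariate, residual variance is proportional to 1 − r², so using headache days in place of the own baseline multiplies it by

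ratio = (1 − r_hd²) / (1 − r_own²).

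The documents give neither correlation for these outcomes. The values below are assumptions; 0.55 is borrowed from headache days. The last column is Φ(2.802/√ratio − 1.960), for a contrast that would have 80% power with the own baseline.

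| r_own | r_hd | variance ratio | SE ratio | power |
|---|---|---|---|---|
| 0.40 | 0.40 | 1.00 | 1.00 | 80% |
| 0.40 | 0.30 | 1.08 | 1.04 | 77% |
| 0.40 | 0.10 | 1.18 | 1.09 | 73% |
| 0.55 | 0.50 | 1.08 | 1.04 | 77% |
| 0.55 | 0.40 | 1.20 | 1.10 | 72% |
| 0.55 | 0.30 | 1.30 | 1.14 | 69% |
| 0.55 | 0.20 | 1.38 | 1.17 | 67% |
| 0.70 | 0.50 | 1.47 | 1.21 | 64% |
| 0.70 | 0.10 | 1.94 | 1.39 | 52% |

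For example, with r_own 0.55 and r_hd 0.3, (1 − 0.09)/(1 − 0.3025) = 0.91/0.6975 = 1.30.

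**3. Check the value of using both.** With q the correlation between the two baselines, R² = (r_own² + r_hd² − 2·r_own·r_hd·q)/(1 − q²). Take q from 0.3 to 0.7 (assumed) and add the own baseline to a model that already holds headache days:

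- r_own 0.55, r_hd 0.2: residual variance falls by 27.5% to 34.3%.
- r_own 0.55, r_hd 0.4: it falls by 17.0% to 24.2%.
- r_own = r_hd = 0.40: it still falls by 3.4% to 10.3%, although swapping one covariate for the other would gain nothing.

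Using both therefore does not depend on which baseline turns out to be the stronger predictor.

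**The case against.** The strongest reply is that nothing has been left out. In the template the covariate is the baseline of the outcome being modelled, and the ANCOVA and HIT-6 models follow the same pattern. Carrying the approach to a new outcome would then naturally mean replacing both the outcome and its baseline. This stands: a reader might infer that the plan discards each outcome's own baseline, but the text shows only that the covariate is not stated. It does not remove the need for a sentence, because no text confirms the intended reading and the template is loosely worded elsewhere. Its reduced model speaks of severe headache although it concerns any headache day, and the follow-up is described as four months although the intervention lasts 12 weeks.

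Other inferences that the documents do not support:

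- *Run-in light-sensitivity days are certainly available.* The text describes the diary as covering headache frequency and severity, and the diary figure is not shown. Daily light sensitivity in the run-in is inferred from the Analysis Plan's description of these outcomes as diary-based. The explicit baseline photophobia measure is a questionnaire.
- *Headache-day frequency says little because all subjects have frequent headache.* The 0.55 correlation came from a subgroup already limited to at least 50% and under 100% headache days, so restriction did not make the covariate uninformative for headache days. Activity-limiting and medicated headache days are subsets of headache days, so their cross-correlation could exceed 0.4. The entry limits also differ within the documents: 8 days a month in the inclusion criteria, 15 days at Visit 2, and 50% in the Safety Monitoring Plan.
- *The variance figure is an established loss.* It rests on assumed correlations. In a logistic GEE a change of covariate also changes the conditional odds ratio being estimated, so the ratios are only indicative.

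**Conclusion.** The point holds as a gap in specification with a possible cost in precision. As written, the GEE reused for these three outcomes names only baseline headache-day frequency, and the plan does not say that each outcome's own run-in proportion enters.

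Under the literal reading, with an own correlation of 0.55 and cross-correlations of 0.2 to 0.4, residual variance would be about 38% to 20% larger than with the own baseline. The loss is nil if the two correlations are equal and reaches a 39% larger standard error at the far end of the assumed range (0.70 and 0.10). All of this is a linear approximation.

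A reader might infer that treatment estimates would be biased by chance baseline differences. They would not be: randomization protects against bias, and chance imbalance is reflected in the standard error. The primary analysis, the HIT-6 analysis and the sample size are unaffected, and the plan says that additional secondary and exploratory results will be interpreted as exploratory. The change is worth making because it costs almost nothing and settles the covariate in advance.

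**What to change.** In item 9, under Other Secondary Outcomes and under the Analysis Plan for Secondary and Exploratory Outcomes, state that the GEE for each diary-proportion outcome adjusts for the proportion of run-in diary days meeting that same criterion, with baseline headache-day frequency kept as a second covariate. For light sensitivity, make this conditional on the run-in diary recording it. Fix the wording before unmasking.

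The cost is a sentence or two in the plan and one more model term per outcome. No new data are needed for severity or medication use; for light sensitivity, check the diary form first.

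A minor side note: "Average Number of Hours Slept per night over the 12-week intervention" is not a proportion of days, and the plan does not say how a 12-week average fits the visit-based mixed model for numeric outcomes. Four-week means at the diary checks might be made to fit, but this is not stated. Assign it a method, such as ANCOVA on the 4-week run-in mean if the diary records sleep.
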